10.3 Discontinued Subjects

10.3.1 Screen Failures

Subjects who were excluded from the study after signing the informed consent and prior to administering treatment are considered screen failures. The Investigator must document the reason for screen failure in the subject's case history source documents.

Subject numbers must not be re-used.

10.3.2 Discontinuations

Discontinued subjects are individuals who voluntarily withdraw or are withdrawn from the study by the Investigator after informed consent is signed and before the last visit is completed.

Subject numbers of discontinued subjects must not be re-used.

Subjects may discontinue from the study or study treatment at any time for any reason. Subjects may also be discontinued from study treatment at any time if, in the opinion of the Investigator, continued treatment poses a risk to their health.

If a subject discontinues from study treatment, every effort must be made to keep the subject in the study and to continue with the study assessments, as specified in the schedule of study procedures and assessments until the final visit.

The Investigator must document the reason for study or treatment discontinuation in the subject's case history source documents.

To ensure the safety of all subjects who discontinue early, Investigators must assess each subject and, if necessary, advise them of any therapies and/or medical procedures that may be needed to maintain their health.

10.3.3 Schedule of Procedures and Assessments for Subjects Discontinued from Investigational Product

Subjects who discontinue the IP (ie, have study lens explanted) will continue in the study through Visit 5A and be followed for safety. At minimum, safety examinations must include the assessments associated with appropriate medical care. Standard post-surgical assessments are bulleted below:

- UCDVA and/or BCDVA
- Slit-lamp Examination
- Dilated Fundus Examination

10.3.4 Subject Lost to Follow Up

If a subject unavoidably misses a scheduled exam, he/she should be rescheduled within the same exam period. The investigational site should show diligence in trying to schedule the subject for all exams. The site must document all attempts to contact the subject in the subject's chart, including dates, times, method of contact, etc. If a subject is unable to return for the Final Study Visit, the Exit Case Report Form should be completed with the appropriate reason for discontinuation indicated. If attempts to contact the subject are unsuccessful, then the Exit Case Report Form for that subject is completed after the last window closes and documented as Lost to Follow-up. The date at which the subject was considered lost to follow-up should also be recorded.

10.4 Subject Pregnant or Lactating

Subjects who become pregnant after having a study IOL implanted (or the study IOL touches the eye) or are lactating during the study will not be discontinued; however, all data from that point forward will be excluded from the BAS analyses because these conditions can alter refraction and visual acuity results. Pregnancy, or women who are lactating, should be noted within the source documentation for each visit, and at which time the subject is pregnant or lactating.

The Investigator must notify the sponsor within 24 hours of learning that a subject is pregnant; reporting procedures are noted in [Section 11.9](#).

10.5 Clinical Study Termination

The Study Sponsor reserves the right to close the investigational site or terminate the study in its entirety at any time.

If the clinical study is prematurely terminated or suspended by the Study Sponsor:

- The Study Sponsor must:
 - Immediately notify the Investigator(s) and subsequently provide instructions for study termination.
 - Inform the Investigator and the regulatory authorities of the termination/suspension and the reason(s) for the termination/suspension.
- The Investigator must:
 - Promptly notify the IRB/IEC of the termination or suspension and of the reasons.
 - Provide subjects with recommendations for post-study treatment options as needed.

The Investigator may terminate the site's participation in the study for reasonable cause.

10.5.1 Follow-up of subjects after study participation has ended

Following this study, the subject will return to their eye care professional for their routine eye care.

10.6 Contingency Measures

To overcome challenges that may arise during unexpected events which could interrupt the conduct of the trial as planned (eg, natural disasters or a public health emergency), contingency measures may be implemented. The intent of contingency measures would be to address the care of enrolled subjects during such unexpected events. It is not expected that contingency measures would affect study design; however, if necessary, the protocol would be amended accordingly. Written notification describing these contingency measures will be provided to the IRB and other regulatory agencies, as applicable. During such events, Investigators must continue to use medical judgement in the care of subjects and follow national and local guidance, as well as IRB reporting requirements. Additional information can be found in the MOP.

11 ADVERSE EVENTS AND DEVICE DEFICIENCIES

11.1 General Information

An adverse event (AE) is any untoward medical occurrence, unintended disease or injury, or untoward clinical signs (including abnormal laboratory findings) in subjects, users, or other persons, whether or not related to the investigational medical device (test product).

Refer to the Glossary of Terms and figures for categories of AEs and SAEs.

Figure 11.1-1 Categorization of All Adverse Events

[figure not shown]
[figure not shown]

Figure 11.1-2 Categorization of All Serious Adverse Events

11.2 Specific Events Relevant to this Protocol

In addition to reporting all AEs (serious and non-serious) meeting the definitions, the PI must report any occurrence of the following as an SAE:

- Cystoid macular edema
- Hypopyon
- Endophthalmitis
- Lens dislocation from posterior chamber
- Pupillary block
- Retinal detachment
- Secondary surgical intervention (excluding Posterior Capsulotomy)

Any other potentially sight-threatening event may also be considered serious based on the judgment of the Investigator and must be reported appropriately as delineated in Section 11.4.

11.2.1 Device Deficiencies

A device deficiency may or may not be associated with subject harm (ie, ADE or SADE); however, not all ADEs or SADEs are due to a device deficiency. The Investigator should determine the applicable category for the identified or suspect device deficiency and report any subject harm separately. Examples of device deficiencies include the following:

- Failure to meet product specifications (eg, incorrect IOLpower)
- IOL defect
- Broken IOL optic
- Broken IOL haptic
- Scratched IOL optic
- Unsealed device packaging
- Suspect product contamination
- Lack of effectiveness

11.3 Monitoring for Adverse Events

At each visit, after the subject has had the opportunity to spontaneously mention any problems, the Investigator should inquire about AEs by asking standard questions such as:

- “Have you had any health problems since your last study visit?”
- “Have there been any changes in the medicines you take since your last study visit?”

Changes in any protocol-specific ocular or systemic parameter evaluated during the study are to be reviewed by the Investigator. Any untoward (unfavorable and unintended) change in a protocol-specific parameter that is clinically relevant, in the opinion of the Investigator, is to

be reported as an AE. These clinically relevant changes will be reported regardless of causality.

11.4 Procedures for Recording and Reporting

AEs are collected from the time of informed consent. Any pre-existing medical conditions or signs/symptoms present in a subject prior to the start of the study (ie, before ICF is signed) are not considered AEs in the study and should be recorded in the Medical History section of the eCRF.

In addition, aqueous cells and flare, corneal edema, raised IOP and superficial punctate keratitis are examples of early post-operative findings that are typically observed following ocular surgery. These are not considered AEs if they can be reasonably expected to resolve within a week and not result in any untoward long term visual outcome impact.

For each recorded event, the ADEs and SAEs documentation must include: date of occurrence, severity, treatment (if applicable), outcome, and assessments of the seriousness and causality. In addition, the Investigator must document all device deficiencies reported or observed with test and control articles on the Device Deficiency eCRF. The site must submit all available information on ADEs, SAEs and device deficiencies to the Study Sponsor immediately as follows:

- ADEs or SAEs are documented on the *Adverse Device Effect and Serious Adverse Event* eCRF within 24 hours of the Investigator's or site's awareness.
- ADEs that do not meet seriousness criteria and device deficiencies must be reported within 10 calendar days of the Investigator's or site's awareness.
- A printed copy of the completed Serious Adverse Event and Adverse Device Effect and/or Device Deficiency eCRF must be included with product returns.
- Additional relevant information after initial reporting is to be entered into the eCRF as soon as the data become available.
- Document any changes to concomitant medications on the appropriate eCRFs.
- Document all relevant information from Discharge Summary, Autopsy Report, Certificate of Death etc., if applicable, in narrative section of the Adverse Device Effect (for related AEs) and Serious Adverse Event eCRF.

NOTE: Should the EDC system become non-operational, the site must complete the appropriate paper *Adverse Device Effect and Serious Adverse Event Form* or *Device Deficiency Form*. The completed form is emailed to the Study Sponsor at

[contact] within 24 hours of the Investigator's or site's awareness; however, the reported information must be entered into the EDC system once it becomes operational.

Study Sponsor representatives and their contact information are provided in the Manual of Procedures that accompanies this protocol.

Further, depending upon the nature of the AE or device deficiency being reported, the Study Sponsor may request copies of applicable portions of the subject's medical records. The Investigator must also report all AEs and device deficiencies that could have led to a SADE according to the requirements of regulatory authorities or IEC/IRB.

11.5 Intensity and Causality Assessments

Where appropriate, the Investigator must assess the intensity (severity) of the AE as mild, moderate, or severe based on medical judgment with consideration of any subjective symptom(s), as defined below:

11.5.1 Intensity (Severity)

Mild An AE is mild if the subject is aware of but can easily tolerate the sign or symptom.

Moderate An AE is moderate if the sign or symptom results in discomfort significant enough to cause interference with the subject's usual activities.

Severe An AE is severe if the sign or symptom is incapacitating and results in the subject's inability to work or engage in their usual activities.

11.5.2 Causality

For every AE in the study, the Investigator must assess the causality (Related or Not Related to the medical device or test procedure). An assessment of causality will also be performed by the Study Sponsor utilizing the same definitions, as shown below:

Related An AE classified as related may be either definitely related or possibly related where a direct cause and effect relationship with the medical device or study procedure has not been demonstrated, but there is a reasonable possibility that the AE was caused by the medical device or study procedure.

Not Related An AE classified as not related may either be definitely unrelated or simply unlikely to be related (ie, there are other more likely causes for the AE).

The Study Sponsor will assess the AEs and may upgrade the Investigator's assessment of seriousness and/or causality. The Study Sponsor will notify the Investigator of any AEs that is upgraded from non-serious to serious or from unrelated to related.

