1 GLOSSARY OF TERMS

Names of test product(s)	Throughout this document, test product(s) will be referred to as PanOptix Toric Trifocal IOL (Models: TFNT30, TFNT40, TFNT50, TFNT60)
Name of Control Product(s)	N/A
Asian Population	Self-identified as being of Chinese, Japanese, Korean, or Mongolian descent.
Adverse Device Effect	Adverse event related to the use of an investigational medical device (test product) or control product. Note: This definition includes adverse events resulting from insufficient or inadequate instructions for use, deployment, implantation, installation, or operation; any malfunction; and use error or intentional misuse of the test product or control product.
Adverse Event	Any untoward medical occurrence, unintended disease or injury, or untoward clinical signs (including abnormal laboratory findings) in subjects, users or other persons, whether or not related to the investigational medical device (test product). Note: For subjects, this definition includes events related to the test product, the control product, or the procedures involved. For users or other persons, this definition is restricted to events related to the test product. Requirements for reporting Adverse Events in the study can be found in Section 11.
Anticipated Serious Adverse Device Effect	Serious adverse device effect which by its nature, incidence, severity, or outcome has been identified in the risk management file.
Device Deficiency	Inadequacy of a medical device with respect to its identity, quality, durability, reliability, safety, or performance. Note: This definition includes malfunctions, use errors, and inadequate labeling.

	Requirements for reporting Device Deficiencies in the study can be found in Section 11.
Enrolled Subject	Any subject who signs an informed consent form for participation in the study.
Interventional Clinical Trial	A research trial that prospectively assigns, whether randomly or not, human participants or groups of humans to one or more health-related interventions to evaluate the effects on health outcomes, and/or a research trial in which diagnostic or monitoring procedures beyond standard of care are conducted and generate outcomes for use in analysis of data.
Malfunction	Failure of a medical device to perform in accordance with its intended purpose when used in accordance with the instructions for use or clinical investigation plan.

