5.3 Statistical Methods for Safety Analyses

5.3.1 Secondary Surgical Interventions

The number and percentage of secondary surgical interventions (SSIs) will be presented for first implanted eyes, second implanted eyes and for all eyes combined in each of the following categories relative to the relationship to IOL:

- 1) Overall
- 2) Related to IOL - due to optical properties
- 3) Related to IOL - not due to optical properties
- 4) Unrelated to IOL

A listing of SSIs will be presented. The listing will include all SSI data with the following variables: Lens model, subject, age, sex, race, specific Asian race, surgery eye, eye, days from surgery, relationship, and description.

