5.3.3 Adverse Events

[figure not shown]
All adverse events (AEs) occurring from when a subject signs informed consent to when a subject exits the study will be accounted for in the reporting. Summary tables for AEs will include the number of affected eyes/subjects, percentage of affected eyes/subjects, 95% two sided confidence intervals, and the number of events. The number and percentage of ocular AEs will be provided for first and second operative eyes and for all eyes. An eye/subject with multiple AEs of the same preferred term will be counted only once toward the total of this preferred term. Listings of AEs will include the lens model, subject ID, Age/Sex, days from surgery, adverse event description, the MedDRA preferred term of the adverse event, and the causality assessment, severity, duration and outcome, when available. Surgery eye and the eye with AE will be provided in the listing of ocular AEs. Adverse events related to the IOL are referred to as adverse device effects (ADE). Listing of pre-treatment AEs, or AEs for non-study eyes will be provided if such cases exist.

Treatment emergent adverse events will be summarized in the following tables and listings:

- Table of All Adverse Events (Serious and Non-Serious Combined)
 - Ocular
 - Non-ocular
- Table of All Adverse Device Effects
 - Ocular
 - Non-ocular
- Table of All Serious Adverse Events (including Serious Adverse Device Effects)
 - Ocular
 - Non-ocular
- Listing of Adverse Event
 - Serious Ocular
 - Serious Non-ocular
 - Non-Serious Ocular
 - Non-Serious Non-ocular

6 Sample Size and Power Calculations

The choice of sample size is not based on statistical considerations.

Approximately 56 subjects will be bilaterally implanted to obtain data for at least 50 subjects (100 eyes) at Month 6, assuming a dropout rate of 10% over a 6 month period. The precision estimates below are presented for individual eye summaries. All eye summaries will have increased precision.

For visual acuity, with a sample size of 50 eyes and assuming a standard deviation of 0.18 logMAR [REDACTED] a two-sided 95%

confidence interval based on large sample z statistics will extend 0.05 logMAR from the observed mean.

[figure not shown]
For residual cylinder, a two-sided 95% confidence interval based on large sample z statistics will extend 0.11 D from the observed mean, assuming a standard deviation of 0.40 D [REDACTED]

[figure not shown]

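### The protocol's causality rule pools the lens with the surgery, so it does not yield the IOL-related category that the SAP reports as adverse device effects

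*Protocol*

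**What the plan says.** **Causality rule (Protocol 11.5.2).** Each AE is classed as "Related or Not Related to the medical device or test procedure". Related covers definite and possible relation; the possible case needs only a "reasonable possibility that the AE was caused by the medical device or study procedure". On the sponsor's side, "An assessment of causality will also be performed by the Study Sponsor utilizing the same definitions". The sponsor may upgrade seriousness or causality; the section describes no step that separates lens from procedure.

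**Form wording (Protocol 11.4).** Supporting records such as discharge summaries are to be documented "in narrative section of the Adverse Device Effect (for related AEs) and Serious Adverse Event eCRF".

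**What an ADE is.** The Protocol Glossary says: "Adverse event related to the use of an investigational medical device (test product) or control product". A note there brings in events from inadequate implantation, among other use problems. SAP 5.3.3 says: "Adverse events related to the IOL are referred to as adverse device effects (ADE").

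**Where the category is used.** SAP 5.3.3 plans a "Table of All Adverse Device Effects", split into ocular and non-ocular. Its SAE table includes serious ADEs, and the AE listings carry the causality assessment.

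**Secondary surgical interventions (SAP 5.3.1).** SSIs have their own attribution to the lens: related through its optical properties, related in another way, or "Unrelated to IOL".

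**The concern.** The category collected is wider than the category reported. Under 11.5.2 the lens and the procedure are alternatives within one definition, so a Related answer does not say which of them was meant. The ADE table needs exactly that distinction.

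This matters because the study has a single arm. No comparator shows how many events the cataract surgery would have produced with another lens, so attribution at the time of assessment is the main way to separate surgical background from lens effect in the AE data. Rates of adverse events are a key safety endpoint, and Protocol 5.2 and 7.2 say that the results will support regional submissions. A reader of the ADE table will take it as a statement about the lens. If attribution is not recorded when the event is assessed, analysts cannot rebuild it reliably. They would have to accept the pooled answer or re-judge each event afterwards in an unmasked study.

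**Working it through.** The documents state no ADE rate and no rate of procedure-related events, so there is no figure to reproduce. The check is a comparison of the rules, followed by a unit calculation.

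**1. The rules side by side**

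| Place | Category | Event caused only by surgery |
|---|---|---|
| Protocol 11.5.2, investigator | Related to device or procedure | Related |
| Protocol 11.5.2, sponsor | Same definitions | Related |
| Protocol 11.4 | ADE form described as for related AEs | Appears to belong on the ADE form |
| Protocol Glossary | ADE: related to use of the device | Not an ADE, unless it arises from inadequate implantation or another listed use problem |
| SAP 5.3.3 | ADE: related to the IOL | Not an ADE |

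The first three rows lead one way and the last two the other. No visible text gives a rule for passing from the first group to the second.

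This reading takes cataract surgery to be a study procedure. Protocol 11.5.2 uses two terms, test procedure and study procedure, and defines neither. Table 3-1, the schedule of study procedures, lists administration of treatment at both surgery visits, which supports the reading.

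**2. Foreseeable cases.** Protocol 5.3.1 names iris trauma, zonular rupture, capsular rupture and detached Descemet's membrane among possible problems during surgery. Some of these can happen before the lens enters the eye. Where one is recorded as an AE, it meets the 11.5.2 definition of Related through the procedure alone.

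**3. An SSI traced through both documents.** Protocol 5.3.1 lists wound leak repair as an SSI.
- Protocol 11.2 requires every SSI other than posterior capsulotomy to be reported as an SAE.
- In the SSI table of SAP 5.3.1, the repair can properly be classed as unrelated to the lens.
- Under Protocol 11.5.2, the same event can be Related through the procedure.
- If Related is carried over to ADE, the event becomes a serious ADE and the two outputs disagree. It is one SAE either way, so the SAE count does not move.

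**4. Size per affected eye.** Inputs: 56 subjects planned for bilateral implantation (Protocol 12.8 and SAP 6), so 56 × 2 = 112 eyes. I assume that the safety set equals these 112 eyes. Each affected eye is counted once.
- All eyes: 1/112 = 0.9 percentage points.
- First eyes or second eyes alone: 1/56 = 1.8 percentage points.

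For k affected eyes and no lens-related event, the all-eye ADE rate is k/112 instead of 0/112. The documents do not give k. The values below are assumed, to show scale only, and are not a forecast. SAP 5.3.3 does not name its interval method; these are exact two-sided 95% limits.

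| k | Rate | 95% limits |
|---|---|---|
| 0 | 0% | 0% to 3.2% |
| 1 | 0.9% | 0.02% to 4.9% |
| 3 | 2.7% | 0.6% to 7.6% |
| 5 | 4.5% | 1.5% to 10.1% |

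**The case against.** A reader might infer that surgery-caused events will be counted against the lens. The documents do not support that as a fact, for these reasons:

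- Read literally, the Glossary and SAP 5.3.3 both keep procedure-only events out of the ADE category. Protocol 11.1 refers readers to the Glossary for AE categories.
- The 11.4 phrase sits in an instruction about narrative documents for a combined ADE and SAE form. It is loose wording, not a derivation rule, and an entry on that form does not by itself make an event an ADE.
- The eCRF and the manual of procedures are not among the documents, and Figures 11.1-1 and 11.1-2 are not shown. The wording of 11.5.2 is compatible with two separate items on the form.
- Some surgery-linked events belong in ADE by definition, because the Glossary includes inadequate implantation.
- SSIs carry their own attribution to the lens.
- Protocol 11.4 already excludes expected early findings, such as raised IOP likely to resolve within a week.
- The all-AE and SAE rates do not depend on causality. No hypothesis or success criterion uses the ADE table. The listings would let a reader pick out many surgical events, and an overcount would be conservative for safety.

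All of this stands, and it limits the point to a risk in a subset of descriptive outputs. It does not remove the mismatch. The correct definitions in the Glossary and the SAP cannot be applied to an answer that does not record which cause was meant. Nor is the direction of error assured: if analysts sort events afterwards from descriptions and preferred terms, lens-related events could also be moved out.

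**Conclusion.** The concern holds as a mismatch between the causality rule and the category reported. As written, Protocol 11.5.2 does not yield the IOL-related events that SAP 5.3.3 tabulates, and 11.4 invites the pooled reading. Procedure-only events can therefore enter the ADE and serious ADE summaries, and the causality shown in the AE listings can conflict with the SSI attribution. The key AE and SAE rates are untouched, and no decision rule is affected; what suffers is the interpretation of the device-specific safety tables.

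The total size cannot be estimated from the documents. The unit is about 0.9 percentage points per affected eye, assuming 112 implanted eyes. The conclusion assumes that cataract surgery counts as a study procedure and that the unseen eCRF, manual and figures do not already separate the two causes. If they do, the data are safe and only the text needs correction.

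**What to change.** 1. In Protocol 11.5.2 and on the AE eCRF, record two separate assessments: related to the IOL or its use (following the Glossary, including inadequate implantation), and related to the surgical procedure. Require both from the investigator and from the sponsor.
2. Align the wording of Protocol 11.4, so that the ADE form refers to device-related events and not to all related events.
3. In SAP 5.3.3, derive ADE and serious ADE from the IOL item only, and show procedure-related events separately.
4. Add a check that the IOL item agrees with the SSI category in SAP 5.3.1 for each SSI reported as an SAE.

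If the eCRF already holds two items, correct 11.5.2 and 11.4 to match it and state the derivation in SAP 5.3.3.

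The cost is one more judgement per AE and, if the form is not already split, an added field, with short edits to the protocol and SAP. No analysis method or sample size changes.
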